Hepatobiliary	
Bilirubin	≥Grade 3, Coincident Direct Bilirubin ≥0.5mg/dl
AST/SGOT and/or ALT/SGPT	≥ Grade 3
	≥Grade 4
Other	
Any Grade 3 non-hematologic toxicity : With the exception of: ≥Grade 3 QTc prolongation (QTc > 500 ms), which is a DLT at any incidence	
Any Grade 4 non-hematologic toxicity	

Any of the following AEs, which when assessed as treatment related, will require patients to be permanently discontinued from study:

- any grade ≥ 3 hemorrhagic event
- 2nd episode of grade ≥ 3 febrile neutropenia
- grade 3 renal toxicity
- grade ≥ 3 QTc prolongation (QTc > 500 ms)
- grade 4 renal toxicity
- grade 4 serum bilirubin with direct bilirubin ≥ 0.5 mg/dL
- grade 4 non-hematologic toxicity

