6.2.7 Dose modification and dose delay

Transfusional support as clinically indicated is also permissible at the discretion of the investigators.

Dose modification rules in Phase I cycles 2-6 (Day 29 - 168) and beyond cycle 7 (Day 169+) or any time in phase II are shown in Table 6.2.3 below. These are to be followed for patients in Phase I as well as Phase II expansion and extension stages. Dose reductions (for PANOBINOSTAT) based on platelet count will be allowed and the dose of PANOBINOSTAT will not go below 5mg PO TIW QOW. See Table 6.2.1/6.2.2 for PANOBINOSTAT and RUXOLITINIB dose levels. The dose of RUXOLITINIB will not be reduced below 5mg PO BID.

Based on the expected occurrence of thrombocytopenia in this patient population with the combination of these agents, we intend to submit a request for agency feedback form to update the safety data in terms of thrombocytopenia after 10 patients have been enrolled on this study. If the safety profile with the combination of PANOBINOSTAT and RUXOLITINIB is acceptable in terms of incidence of platelet count below $20 \times 10^9/L$ and grade 3 or higher bleeding events, then we will continue the study with a threshold of $20 \times 10^9/L$ for dose holding/modification. If there is a single incidence of grade 3 or higher bleeding in association with a platelet count of $<35 \times 10^9/L$, then this threshold will be modified accordingly. This determination will be made after review by the FDA.

Table 6.2.1 RUXOLITINIB dose levels for dose modifications in Cycles 2+ (day 29+)

Dose level	RUXOLITINIB	Comment
-1	5mg PO BID	Lowest dose allowed in the study
0	10mg PO BID	Starting dose in induction phase for all patients on study
1	15mg PO BID	Starting dose for cohort 4a, 4b

Table 6.2.2 PANOBINOSTAT dose levels for dose modifications in Cycles 2+ (day 29+)

Dose level	PANOBINOSTAT	Cumulative dose (per cycle)	Comment
-1	5mg PO TIW QOW	30mg	Lowest allowable dose on the study
0	10mg PO TIW QOW	60mg	Starting dose of cohort 1
1	15mg PO TIW QOW	90mg	Starting dose for cohort 2, 4a
2	20mg PO TIW QOW	120mg	Starting dose for cohort 3, 4b
3	10mg PO TIW QW	120mg	Starting dose for cohort 5
4	15mg PO TIW QW	180mg	Starting dose for cohort 6
5	20mg PO TIW QW	240mg	Maximum dose allowed in study

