Dose modifications or interruptions for adverse events occurring during the DLT-definition period (Cycle 1 Day 1 through Cycle 1 Day 28 of Phase I), and considered as treatment-related will not be allowed. This would require removal of a patient with a DLT within Day 1-28 of Phase I.

Beginning in cycle 2 (day 29), patients who do not tolerate the protocol-specified dosing schedule are permitted to dose adjust in order to allow the patient to continue the study treatment. Tables 6.2.1 and 6.2.2 outline the possible dose level reductions permitted depending on the current dose of each drug at the time of the AE. Patients who experience toxicity at either a dose of RUXOLITINIB at 5mg PO BID or PANOBINOSTAT at 5mg PO TIW QOW cannot be dose reduced further and will be removed from study. Table 6.2.3 and Table 6-4 provide instruction on management per toxicity. All dose modifications should be based on the worst preceding toxicity (CTCAE version 4.0). Patients who require dose hold of RUXOLITINIB are allowed to receive steroids (prednisone, dexamethasone, etc) as per the Investigators discretion to avoid or blunt potential RUXOLITINIB-withdrawal syndrome.

All adverse events should be treated as per the local standard of care and referred to a specialist if clinically indicated. Investigators can use their discretion when making dose-reduction decisions unless otherwise specified in the guidelines below.

If at any time during the study period the use of a strong CYP3A4 inhibitor becomes necessary to treat the patient, a dose modification for RUXOLITINIB is necessary. See Section 6.3 for permitted or prohibited concomitant medications for this study. Also see Section 6.3.4 for dose modification schema for RUXOLITINIB.

Table 6.2.3 Criteria for dose modifications of RUXOLITINIB and PANOBINOSTAT due to study drug-related toxicity from Day 29 and beyond in Phase I or anytime in Phase II (see Table 6-6 for QT prolongation dose management)

Worst Toxicity CTCAE Grade* unless otherwise specified (Value)	Dose Modification Guidelines At any time during a cycle of therapy (including intended day of dosing)	
HEMATOLOGICAL TOXICITIES		
Thrombocytopenia	< 20 x 10 ⁹ /L	Interrupt study treatment dosing until resolved to ≥ 20 x 10 ⁹ /L, then restart study treatment at reduced level as per Table 6.2.1/6.2.2.

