	> 20 x 10 ⁹ /L + grade 3 bleed	Interrupt study treatment dosing until bleeding is resolved and platelet count is at level before bleed was noted, then resume study treatment at reduced level as per Table 6.2.1/6.2.2
Neutropenia (ANC)	Grade 4 (ANC < 0.5 x 10 ⁹ /L)	Interrupt study treatment dosing until resolved to ≤ grade 2, or baseline, then: 
 • If resolved within 7 days restart study treatment at an unchanged dose level • If resolved in more than 7 days then restart study treatment at reduced level as per Table 6.2.1/6.2.2
	Febrile neutropenia (ANC < 1.0 x 10 ⁹ /L, fever ≥ 38.5°C)	Interrupt study treatment dosing until fever resolved and ANC ≤ grade 2, then restart study treatment at reduced level as per Table 6.2.1/6.2.2
Anemia[#] only requires dose reductions after cycle 6 (day 169+)	Doubling of transfusion frequency from baseline or hemoglobin 2g/dL below baseline (screening period)	Hold PANOBINOSTAT only and continue RUXOLITINIB, if hemoglobin (or transfusion frequency) returns to baseline within 28 days restart PANOBINOSTAT at same dose, if this recurs again then reduce dose as per TABLE 6.2.1/6.2.2
NON-HEMATOLOGICAL TOXICITIES		
CARDIAC		
Cardiac - Prolonged QT interval**	Please refer to Table 6-6, Section 6.2.8 and Section 7.2.7.	

Worst Toxicity CTCAE Grade* unless otherwise specified (Value)		Dose Modification Guidelines At any time during a cycle of therapy (including intended day of dosing)
GASTROINTESTINAL		
Diarrhea	Grade 2 (4-6 stools/day over baseline, etc) despite the use of optimal anti-diarrheal medications	Hold PANOBINOSTAT dosing until resolved to \leq grade 1, or baseline, then restart at unchanged dose level
	Grade 3 (\geq 7 stools/day over baseline, etc) despite the use of optimal antidiarrheal medications	Hold PANOBINOSTAT dosing until resolved to \leq grade 1, or baseline, then restart study treatment at reduced level as per Table 6.2.2
	Grade 4 (life-threatening consequences, hemodynamic collapse, etc) despite the use of optimal antidiarrheal medications	Permanently discontinue study treatment dosing
Vomiting/Nausea***	Grade 1 & 2 not requiring treatment or controlled using standard anti-emetics	Maintain dose level
	Grade 3 or 4 vomiting or Grade 3 nausea that cannot be controlled despite the use of standard anti-emetics	Interrupt study treatment dosing until resolved to \leq grade 1, or baseline, then restart study treatment at reduced level as per Table 6.2.1/6.2.2
Fatigue		

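### A treatment-related grade 3 bleed with platelets above 20 x 10⁹/L ends participation under Section 6.2.5 but is to be held and resumed under Table 6.2.3, and no rule says which prevails

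*Combined protocol and SAP*

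**What the plan says.** Two parts of the combined protocol and SAP govern the same event.

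- **Section 6.2.5, list after Table 6-3.** The lead-in is "Any of the following AEs, which when assessed as treatment related, will require patients to be permanently discontinued from study", and the first of its seven items is "any grade ≥ 3 hemorrhagic event". Neither carries a day, phase or platelet limit.
- **Section 6.2.7, Table 6.2.3.** The title limits the table to dose changes "due to study drug-related toxicity from Day 29 and beyond in Phase I or anytime in Phase II". Under Thrombocytopenia, the row for "> 20 x 10 ⁹ /L + grade 3 bleed" instructs: "Interrupt study treatment dosing until bleeding is resolved and platelet count is at level before bleed was noted, then resume study treatment at reduced level". The text of Section 6.2.7 says of these rules: "These are to be followed for patients in Phase I as well as Phase II expansion and extension stages".

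Section 6.2.7 also anticipates such bleeds. A passage beginning "If there is a single incidence of grade 3 or higher bleeding in association with a platelet count of" goes on to name 35 x 10⁹/L, and says that the platelet threshold for holding doses would then be changed after FDA review.

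The nearest thing to a precedence rule is a sentence in Section 6.2.7. It gives investigators discretion over dose reductions where the guidelines that follow do not specify otherwise. It does not rank Section 6.2.5 against the table.

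**The concern.** The stop list and the table appear to give opposite mandatory instructions after a serious bleed: leave the study for good, or return to treatment at a lower dose. The drugs share thrombocytopenia as their principal overlapping dose-limiting toxicity (Section 1.4.2), so the issue is re-exposure to the likely cause. A bleed with platelets between 20 and 35 x 10⁹/L would both trigger the threshold review and fall in the disputed row. The trial has no data monitoring committee (Section 8.6) and no site monitoring (Section 9.1), so no independent body would settle the matter as cases arise. Section 12 sends any intended departure from the protocol to an amendment.

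**Working it through.** No arithmetic applies, and the plan states no figure to reproduce. The check compares the two rules on each condition.

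| Condition | Section 6.2.5 list | Table 6.2.3 row |
|---|---|---|
| Event | Hemorrhage, grade 3 or higher | Grade 3 bleed, under Thrombocytopenia |
| Attribution | Event judged treatment related | Toxicity related to study drug (table title) |
| Platelets | Any count | Above 20 x 10⁹/L |
| Time | No limit stated | Day 29 onward in Phase I; any time in Phase II |
| Action | Permanent discontinuation from study | Hold, then resume at a reduced level |

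**1. Overlap.** A grade 3 bleed judged treatment related, with platelets above 20 x 10⁹/L and inside the table's time window, meets every condition in both columns. A patient permanently off study cannot resume study treatment, so the actions are incompatible.

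**2. Time window.** The list sits in the section that defines DLTs, so it might be thought to cover only Days 1 to 28 of Phase I. Two things count against that. Section 6.2.5 states the 28-day limit expressly for DLTs but not for the list. The list also includes a second febrile neutropenia of grade 3 or higher. In Days 1 to 28 of Phase I a first related episode is already a DLT (Table 6-3) and requires removal (Section 6.2.7), so the second-episode item has work to do only outside that window.

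**3. Where there is no conflict.** In Days 1 to 28 of Phase I, Section 6.2.7 forbids interruption or modification for treatment-related events, and Table 6.2.3 does not yet apply.

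**4. Attribution.** The table's relatedness condition can attach to the thrombocytopenia, while the list requires the bleed itself to be related. Drug-related thrombocytopenia with a bleed judged unrelated therefore fits the row and not the list. The conflict is confined to bleeds judged related.

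**5. Other restart text.** Six further places restart treatment without referring to the list:
- the row for platelets below 20 x 10⁹/L, which says "Interrupt study treatment dosing until resolved to ≥ 20 x 10 ⁹ /L, then restart study treatment at reduced level" and does not mention bleeding;
- febrile neutropenia, with no limit on episodes;
- grade 4 vomiting;
- grade 4 bilirubin, whatever the direct fraction;
- AST/ALT, where the top row (above 10 x ULN) has no ceiling; the documents do not give the CTCAE grade 4 cut-off, but the highest values must fall there;
- Section 6.2.7.1, which reaches grade 3 or 4 renal events and other unlisted grade 4 non-hematologic events.

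In each of these the restart text is broader than the stop item. Grade 4 diarrhea is consistent, because the table also stops treatment permanently. QTc above 500 ms has its own rule in Table 6-4, whose post-dose instruction also discontinues.

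**The case against.** The strongest reply is that a safe and compliant action always exists. Sections 6.1.4, 6.2.9 and 7.1.5.1 let the investigator stop whenever that is in the patient's interest, Section 6.2.7 describes dose adjustment as permitted, and the table column is headed as guidelines. Resumption also requires that the bleed has resolved, platelets have recovered and the dose is reduced.

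Much of this stands. A reader might infer that the investigator breaches the protocol whichever rule is followed. The documents do not support that, because stopping is always allowed; the breach runs one way only, when treatment is resumed. The permission to stop does not remove the conflict, though. It does not authorize continuing against Section 6.2.5, and Section 6.2.7 says the table's rules are to be followed.

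A reader might also infer that the row can never be reconciled with the list. That is too strong, because the row validly covers a bleed judged unrelated.

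Finally, a reader might count seven contradictions by adding the six overlaps. On an ordinary reading a specific stop item limits broader restart text, so those six are loose drafting. The grade 3 bleed row differs because it names a grade 3 bleed explicitly and still says to resume.

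**Conclusion.** The point holds for one table row. From Day 29 in Phase I and at any time in Phase II, a grade 3 bleed judged treatment related with platelets above 20 x 10⁹/L must end participation under Section 6.2.5, yet Table 6.2.3 says to hold and resume. No precedence is stated. This is a contradictory safety rule and should be fixed, but the harm is limited because stopping is always open to the investigator.

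The conclusion rests on the list applying beyond the DLT window, which the second-episode item supports, and on the bleed itself being judged related. The size in patients is unknown, because the documents give no bleeding rate for the combination. Section 1.2.3 reports no grade 3 or 4 bleed among the 13 MF patients on single-agent panobinostat in one study, which gives no rate for two drugs together. The documents do not support a claim that patients were harmed or that any planned analysis is affected.

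**What to change.** Make one text amendment with two parts.

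1. State in Section 6.2.5 that the list applies throughout Phase I and Phase II and overrides Table 6.2.3 and Section 6.2.7.1. This sentence also settles the six broader restart texts, so they need no row-by-row edits.
2. Change the row for a grade 3 bleed with platelets above 20 x 10⁹/L to permanent discontinuation when the bleed is treatment related. Keep hold-and-resume only for a bleed judged unrelated.

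If the investigators do want rechallenge after a related bleed, the consistent alternative is to take that event off the list.

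The change needs no extra data, visits or patients and leaves the analysis as it is. The cost is that a few patients lose rechallenge, and forced stopping carries a risk of ruxolitinib withdrawal syndrome (Section 1.3.3 cites 5 of 47 patients). The taper sentence in Section 6.2.10 covers stopping for reasons other than hematologic safety, so it may not reach a bleed with thrombocytopenia. The sentence after it lets the investigator manage withdrawal with any treatment, and the amendment could point there.

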6.2.6 Follow-up for toxicities

Patients whose treatment is interrupted or permanently discontinued due to an adverse event or abnormal laboratory value must be followed at least once a week for 4 weeks up to day 28. Patients whose treatment is interrupted or permanently discontinued due to an SAE, must be followed at least once a week for 4 weeks up to day 28, and subsequently at 4-week intervals, until resolution or stabilization of the event, whichever comes first. If a patient requires a dose delay for either drug for longer than 90 days from the intended day of the next scheduled dose, then the patient must be discontinued from the study. Hematology labs (CBC) and pertinent non-hematology labs will be part of the follow up procedures. ECG will also be part of the follow up procedures if the AE/SAE was cardiac related.

All patients will be followed for AE's and SAE's for 30 days following the last dose of study treatment, with the exception of prolonged QTc.

6.2.7 Dose modification and dose delay

Transfusional support as clinically indicated is also permissible at the discretion of the investigators.

Dose modification rules in Phase I cycles 2-6 (Day 29 - 168) and beyond cycle 7 (Day 169+) or any time in phase II are shown in Table 6.2.3 below. These are to be followed for patients in Phase I as well as Phase II expansion and extension stages. Dose reductions (for PANOBINOSTAT) based on platelet count will be allowed and the dose of PANOBINOSTAT will not go below 5mg PO TIW QOW. See Table 6.2.1/6.2.2 for PANOBINOSTAT and RUXOLITINIB dose levels. The dose of RUXOLITINIB will not be reduced below 5mg PO BID.

Based on the expected occurrence of thrombocytopenia in this patient population with the combination of these agents, we intend to submit a request for agency feedback form to update the safety data in terms of thrombocytopenia after 10 patients have been enrolled on this study. If the safety profile with the combination of PANOBINOSTAT and RUXOLITINIB is acceptable in terms of incidence of platelet count below $20 \times 10^9/L$ and grade 3 or higher bleeding events, then we will continue the study with a threshold of $20 \times 10^9/L$ for dose holding/modification. If there is a single incidence of grade 3 or higher bleeding in association with a platelet count of $<35 \times 10^9/L$, then this threshold will be modified accordingly. This determination will be made after review by the FDA.

Table 6.2.1 RUXOLITINIB dose levels for dose modifications in Cycles 2+ (day 29+)

Dose level	RUXOLITINIB	Comment
-1	5mg PO BID	Lowest dose allowed in the study
0	10mg PO BID	Starting dose in induction phase for all patients on study
1	15mg PO BID	Starting dose for cohort 4a, 4b

Table 6.2.2 PANOBINOSTAT dose levels for dose modifications in Cycles 2+ (day 29+)

Dose level	PANOBINOSTAT	Cumulative dose (per cycle)	Comment
-1	5mg PO TIW QOW	30mg	Lowest allowable dose on the study
0	10mg PO TIW QOW	60mg	Starting dose of cohort 1
1	15mg PO TIW QOW	90mg	Starting dose for cohort 2, 4a
2	20mg PO TIW QOW	120mg	Starting dose for cohort 3, 4b
3	10mg PO TIW QW	120mg	Starting dose for cohort 5
4	15mg PO TIW QW	180mg	Starting dose for cohort 6
5	20mg PO TIW QW	240mg	Maximum dose allowed in study

Dose modifications or interruptions for adverse events occurring during the DLT-definition period (Cycle 1 Day 1 through Cycle 1 Day 28 of Phase I), and considered as treatment-related will not be allowed. This would require removal of a patient with a DLT within Day 1-28 of Phase I.

Beginning in cycle 2 (day 29), patients who do not tolerate the protocol-specified dosing schedule are permitted to dose adjust in order to allow the patient to continue the study treatment. Tables 6.2.1 and 6.2.2 outline the possible dose level reductions permitted depending on the current dose of each drug at the time of the AE. Patients who experience toxicity at either a dose of RUXOLITINIB at 5mg PO BID or PANOBINOSTAT at 5mg PO TIW QOW cannot be dose reduced further and will be removed from study. Table 6.2.3 and Table 6-4 provide instruction on management per toxicity. All dose modifications should be based on the worst preceding toxicity (CTCAE version 4.0). Patients who require dose hold of RUXOLITINIB are allowed to receive steroids (prednisone, dexamethasone, etc) as per the Investigators discretion to avoid or blunt potential RUXOLITINIB-withdrawal syndrome.

All adverse events should be treated as per the local standard of care and referred to a specialist if clinically indicated. Investigators can use their discretion when making dose-reduction decisions unless otherwise specified in the guidelines below.

If at any time during the study period the use of a strong CYP3A4 inhibitor becomes necessary to treat the patient, a dose modification for RUXOLITINIB is necessary. See Section 6.3 for permitted or prohibited concomitant medications for this study. Also see Section 6.3.4 for dose modification schema for RUXOLITINIB.

Table 6.2.3 Criteria for dose modifications of RUXOLITINIB and PANOBINOSTAT due to study drug-related toxicity from Day 29 and beyond in Phase I or anytime in Phase II (see Table 6-6 for QT prolongation dose management)

Worst Toxicity CTCAE Grade* unless otherwise specified (Value)	Dose Modification Guidelines At any time during a cycle of therapy (including intended day of dosing)	
HEMATOLOGICAL TOXICITIES		
Thrombocytopenia	< 20 x 10 ⁹ /L	Interrupt study treatment dosing until resolved to ≥ 20 x 10 ⁹ /L, then restart study treatment at reduced level as per Table 6.2.1/6.2.2.
	> 20 x 10 ⁹ /L + grade 3 bleed	Interrupt study treatment dosing until bleeding is resolved and platelet count is at level before bleed was noted, then resume study treatment at reduced level as per Table 6.2.1/6.2.2
Neutropenia (ANC)	Grade 4 (ANC < 0.5 x 10 ⁹ /L)	Interrupt study treatment dosing until resolved to ≤ grade 2, or baseline, then: 
 • If resolved within 7 days restart study treatment at an unchanged dose level • If resolved in more than 7 days then restart study treatment at reduced level as per Table 6.2.1/6.2.2
	Febrile neutropenia (ANC < 1.0 x 10 ⁹ /L, fever ≥ 38.5°C)	Interrupt study treatment dosing until fever resolved and ANC ≤ grade 2, then restart study treatment at reduced level as per Table 6.2.1/6.2.2
Anemia[#] only requires dose reductions after cycle 6 (day 169+)	Doubling of transfusion frequency from baseline or hemoglobin 2g/dL below baseline (screening period)	Hold PANOBINOSTAT only and continue RUXOLITINIB, if hemoglobin (or transfusion frequency) returns to baseline within 28 days restart PANOBINOSTAT at same dose, if this recurs again then reduce dose as per TABLE 6.2.1/6.2.2
NON-HEMATOLOGICAL TOXICITIES		
CARDIAC		
Cardiac - Prolonged QT interval**	Please refer to Table 6-6, Section 6.2.8 and Section 7.2.7.	

Worst Toxicity CTCAE Grade* unless otherwise specified (Value)		Dose Modification Guidelines At any time during a cycle of therapy (including intended day of dosing)
GASTROINTESTINAL		
Diarrhea	Grade 2 (4-6 stools/day over baseline, etc) despite the use of optimal anti-diarrheal medications	Hold PANOBINOSTAT dosing until resolved to \leq grade 1, or baseline, then restart at unchanged dose level
	Grade 3 (\geq 7 stools/day over baseline, etc) despite the use of optimal antidiarrheal medications	Hold PANOBINOSTAT dosing until resolved to \leq grade 1, or baseline, then restart study treatment at reduced level as per Table 6.2.2
	Grade 4 (life-threatening consequences, hemodynamic collapse, etc) despite the use of optimal antidiarrheal medications	Permanently discontinue study treatment dosing
Vomiting/Nausea***	Grade 1 & 2 not requiring treatment or controlled using standard anti-emetics	Maintain dose level
	Grade 3 or 4 vomiting or Grade 3 nausea that cannot be controlled despite the use of standard anti-emetics	Interrupt study treatment dosing until resolved to \leq grade 1, or baseline, then restart study treatment at reduced level as per Table 6.2.1/6.2.2
Fatigue		
Fatigue	Grade 3	Hold PANOBINOSTAT dosing until resolved to \leq grade 2, or baseline, then: 
 • If resolved within 7 days after suspending study treatment, then restart at unchanged dose level • If resolved in more than 7 days after suspending study treatment, then restart study treatment at reduced level as per Table 6.2.1/6.2.2
HEPATIC		
Total Bilirubin	Grade 3 or 4	Interrupt study treatment dosing until resolved to \leq grade 2, or baseline, then restart study treatment at reduced level as per Table 6.2.1/6.2.2
Note: If Grade 3 or Grade 4 hyperbilirubinemia is due to the indirect component only, and hemolysis as the etiology has been ruled out as per institutional guidelines (e.g., review of peripheral blood smear and haptoglobin determination), then reduction of one dose level and continuation of treatment is at the discretion of the Investigator.		

Worst Toxicity CTCAE Grade* unless otherwise specified (Value)		Dose Modification Guidelines At any time during a cycle of therapy (including intended day of dosing)
AST/SGOT, ALT/SGPT	> 5-10 x ULN	Interrupt study treatment dosing until resolved to \leq grade 1 (or \leq grade 2 if liver infiltration with tumor is present), or baseline, then: 
 • If resolved within 7 days, then: 
 • restart study treatment at unchanged dose level • If resolved in more than 7 days, then restart study treatment at reduced level as per Table 6.2.1/6.2.2.
	> 10 x ULN	Interrupt study treatment dosing until resolved to \leq grade 1, or baseline, then: 
 • restart study treatment at reduced level as per Table 6.2.1/6.2.2.
All dose modifications should be based on the worst preceding toxicity.		
* Common Terminology Criteria for Adverse Events (CTCAE Version 4.0)		
** It is critical that electrolyte abnormalities be followed closely and corrected prior to dosing		
*** See also concomitant medication Section 6.3.		

# Management of anemia
 
Prior experience with RUXOLITINIB and PANOBINOSTAT as single agents in patients with myelofibrosis suggest that worsening anemia can be treated with PRBC transfusions, and will eventually resolve within 4-6 months without other interventions (LBH589BUS58, LBH589BUS32T). Interestingly, the decrease in spleen size observed in the PANOBINOSTAT responders was accompanied by increases in hemoglobin by at least 2 g/dL (LBH589BUS58).
 
Dose modifications specifically for anemia should be implemented after cycle 6 if the rate of transfusion has significantly increased, and continues without improvement as compared to baseline. Following day 168, patients can be placed in dose hold of the PANOBINOSTAT (up to 28 days) to allow for hemoglobin to return to baseline, after which the study treatment should then be resumed at the same level. If after resumption of PANOBINOSTAT, worsening anemia recurs, then dose modifications according to Table 6.2.1/6.2.2 will be followed.
 
If after holding PANOBINOSTAT for 28 days the patient's hemoglobin has not returned to baseline, but attained a clinically acceptable hemoglobin level, dose modifications according to Tables 6.2.1/6.2.2 can be followed. If after a dose hold of study treatment for 28 days a clinically acceptable hemoglobin value has not been reached the patient must be discontinued from study treatment.
		

If a patient experiences new (or treatment emergent) grade 2 non-hematologic adverse event(s) considered at least possibly related to study treatment, and which the patient finds intolerable or in the Investigator's judgment is/are not acceptable, treatment should be held

until the adverse event(s) resolves to CTCAE grade 1. Study treatment may then be restarted at the same dose and schedule. If the same intolerable grade 2 adverse event(s) occurs again, study treatment should again be temporarily discontinued until the toxicity resolves to \leq CTCAE grade 1. Study treatment should then be restarted at a reduced dose level as per Tables 6.2.1/6.2.2. At the discretion of the Investigator, patients with grade \geq 2 adverse events of major organs (e.g., heart, lungs, CNS) may be discontinued from further study therapy without being retreated with a dose reduction.

